March 15, 2018	
 • 5.2 Added to the paragraph "Women or girls of childbearing potential should not get pregnant prior to their surgery nor after. The stress of surgery, the general anesthetic and the effect of different medication including clonidine may alter the natural development of a new born. You should use a proven birth control method (such as Contraceptive Pill, a diaphragm) or abstain from having sex for the 6 months that you are taking part in the study". • 7.2 Changes to exclusion criteria 
 ○ Children with history of allergies to Clonidine or its excipients in either injection or tablet formulation (see respective monograph) ○ Children with history of galactose intolerance ○ Children with history of myocardial disease, arrhythmias, cerebrovascular disease, Raynaud's/Thromboangiitis obliterans or chronic renal failure diagnosed based on history and physical ○ Pregnancy excluded by an in hospital testing the night before surgery

	
○• 9.1 Clarification of pain rating scale and addition of Medical History Interview Form previously omitted in error; Individual QST tests added in brackets (MDT,PPT,CPM)• 9.2 1 – Clonidine Arm - Administration of study agent given post-surgery and not before surgery; Clarification that Anesthesia Data Collection and SDST Data Collection will be completed at this time point point; Clarification that level of drowsiness will be collected on Sedation Level Form); Clarification that Neurological Deficit Post Op form will be collected at this time;• 9.2.2 – Placebo Arm - Administration of study agent will be given post-surgery and not before surgery.• 9.3 Correction to questionnaires to be completed by patients in-hospital; to be completed on days 1, 2 & 5, not every day; PSQI (In-Hospital questionnaire was previously omitted by error, now added.• 9.3.1 amended to read dosage to 100 mcg Clonidine from Clonidine and removed (between 50 mcg to 100 mcg as prescribed based on the weight of the patient)• 9.5 Added Medical History Interview (Patient History – REVISIT Collection Form) – previously omitted in error• 9.5.1 Additional details for unscheduled visits were added concerning tests/and or data to be collected at unscheduled visits.
--	---

PROTOCOL SIGNATURE PAGE

Protocol Title:

Sensorial and physiological mechanism-based assessments of perioperative pain

11.2.4 QST THERMAL FAMILIARIZATION PRE-TEST	32
12 PAIN ASSESSMENT QUESTIONNAIRES	34
12.1 In-Hospital Additional Measures:.....	35
12.1 STUDY PLAN TABLE	35
13. SUBJECT SAFETY	36
13.1 SAFETY AND TOXICITY ASSESSMENT	36
13.2 ADVERSE EVENT AND ADVERSE DRUG REACTION (adr).....	36
13.3 SERIOUS ADVERSE EVENT OR ADVERSE DRUG REACTION	37
13.4 ANTICIPATED ADVERSE DRUG REACTIONS.....	37
13.5 SERIOUS ADVERSE EVENT AND ADVERSE DRUG REACTION REPORTING	39
13.6 NOTIFYING HEALTH CANADA	39
13.7 UNBLINDING PROCEDURE	40
14 DATA HANDLING AND RECORD KEEPING	41
14.1 CONFIDENTIALITY AND SECURITY.....	41
14.2 QUALITY CONTROL AND QUALITY ASSURANCE.....	41
14.3 DATA STORAGE.....	41
14.4 CONFIDENTIALITY AND SECURITY.....	41
14.5 SOURCE DOCUMENTATION.....	42
14.6 RECORD RETENTION	43
15 QUALITY CONTROL AND QUALITY ASSURANCE.....	43
15.1 DATA SAFETY MONITORING BOARD (DSMB)	43
15.2 STUDY MONITORING PLAN	43

16 STATISTICAL CONSIDERATIONS	44
16.1 PRIMARY STUDY ENDPOINTS.....	44
16.2 SECONDARY ENDPOINTS	44
16.3 SAMPLE SIZE DETERMINATION AND POWER / ACCRUAL RATE	44
16.4 STATISTICAL METHODS.....	44
16.5 STRATIFICATION FACTORS.....	45
17 FINANCE.....	45
18 REFERENCES	45

Study Summary

Title	Sensorial and physiological mechanism-based assessments of perioperative pain
Short Title	RCT
Methodology	Randomized-controlled double-blind study
Study Duration	5 years
Study Site(s)	Shriners Hospital for Children Canada
Objectives	The overall goal of this proposal is to determine if quantitative sensory testing (QST) assessing pain modulation can be used as a clinical tool to optimize perioperative pain management. The central hypothesis is that the identification of patient's sensory pain profile allows personalizing therapeutic approaches to improve individualized pain management and thus prevents pain chronicity.
Number of Subjects	150 (approximately 75 for each arm)
Diagnosis and Main Inclusion Criteria	Female patients between 10 and 21 years old with a diagnosis of Adolescent Idiopathic Scoliosis (AIS) and no concomitant diseases, who are scheduled for scoliosis surgery at the Shriners Hospital, will be invited to participate in the study.
Study Product, Dose, Route, Regimen	Arm 1 - Intrathecal Clonidine after to surgery & PO Clonidine for 5 days post-op
Duration of administration	Day of surgery and 5 days post-operatively.
Reference therapy	Arm 2 - Intrathecal Morphine after to surgery & PO Placebo for 5 days post-op
Statistical Methodology	Descriptive statistics (means, SD, medians, n, %) will be calculated in order to present baseline characteristics of the different comparison groups and follow-up measures. To better appreciate the evolution of pain intensity (primary endpoint) during the longitudinal follow-up (baseline to six months after surgery), linear mixed models for repeated measures will be achieved for each of the three comparison schemes.

Study Schema

1 INTRODUCTION & BACKGROUND

Thousands of children undergo surgery across the Shriners system each year. These children are at a particularly high risk of suffering significant pain as many of the orthopedic surgical procedures are invasive. Under-treated postoperative pain in children leads to increased postoperative morbidity [1] and can have a negative impact on all aspects of health related quality of life including physical (e.g., reduced quality of sleep, delayed mobilization), emotional (e.g., anxiety, distress, negative thoughts), reduced social interactions with friends and family and school absenteeism [2]. Postoperative pain has immediate consequences leading to postoperative morbidity [1] Moreover, between 10 to 20 % of children undergoing surgery will develop chronic postsurgical pain (CPSP), making this problem the most common surgical complication [3,4]. Preventing CPSP becomes highly relevant as it may predispose children to experience recurrent pain during adulthood [5,6]. The clinical challenge rests in the ability to determine which patient will be at risk of having poor postoperative pain control and the development of CPSP. The challenge is even more relevant as to which analgesic protocol will best relieve pain for a specific patient. In this context, it is of high relevance to provide clinicians a tool to identify patients at risk of having poor postoperative pain control and CPSP. Ideally the tool should provide a rational (physiological/mechanistic based) approach to the establishment of a personalized analgesic perioperative protocol.

With over 5 million children undergoing surgery yearly, and 25% of adults referred to chronic pain clinics identifying surgery as the antecedent, there is a crying need to elucidate factors that predispose to chronic postoperative pain in children [7]. The nature of orthopedic surgery places our patients at particular risk of experiencing severe pain. Our procedures often consist of detaching and/or cutting muscles, exposing, manipulating and cutting bone. The periosteum, a highly innervated tissue [8] is often stripped, cut and/or crushed, thus inducing significant postoperative pain. In addition, many neural elements are in close proximity of the surgical field placing these patients at high risk of experiencing neuropathic pain. Such tissue manipulation causes a cascade of neurochemical, inflammatory, and hormonal responses that trigger pain and impact physical outcomes such as wound healing and mobilization [9]. Surgery-induced peripheral neural activation and central modulation may determine pain intensity at the early postoperative stage [10]. Thus, tissue injury may set up the neuronal mechanisms for the development of an eventual chronic state. Evidence suggests that acute postoperative pain is a major risk factor for the development of persistent postoperative pain [11,12].

2 INVESTIGATIONAL ASSESSMENT

2.1 QUANTITATIVE SENSORY TESTING (QST)

QST refers to the assessment of the somatosensory function that may be of clinical interest with a great variety of procedures that have specific quantification of one particular aspect of sensory function (Rolle, Baron et al. 2006). QST provides additional information on the mechanisms involved in pain transduction, modulation and in patient's perception and expectation of pain (Goffaux, Lafrenaye et al. 2008, Morin, Marchand et al. 2014), leading to mechanism-based pain management. Two central mechanisms commonly assessed in the experimental setting through QST are the temporal summation (TS) and conditioning pain modulation (CPM). Several studies in various surgical settings have demonstrated a predictive effect of QST parameters. Weissman-Fogel et al. (2009) reported that enhanced pre-surgical TS, a psychophysical correlate of wind-up

and reflecting central sensitization (Arendt-Nielsen and Petersen-Felix 1995), and higher pain scores for mechanical stimulation were significantly associated with greater postoperative intensity in adults after thoracotomy surgery, suggesting that individual susceptibility toward a greater summation response may characterize patients who are potentially vulnerable to augmented postoperative pain (Weissman-Fogel, Granovsky et al. 2009). Preoperative TS level may also be a mechanistic predictor for the development of chronic postoperative pain as studied in adult patients after TKR surgery (Petersen, Arendt-Nielsen et al. 2015). Yarnitsky et al. (2008) demonstrated that efficient preoperative CPM predicted lower risk of chronic post-thoracotomy pain in adult patients (Yarnitsky, Crispel et al. 2008). Furthermore, early postoperative QST testing has also been reported to predict long-term pain outcome. Surgery-induced peripheral neural activation and central neuroplastic changes may determine postoperative pain intensity. Adult patients who developed moderate-to-severe pain following surgery had pronociceptive changes (TS) compared with patients who developed mild pain (Petersen, Arendt-Nielsen et al. 2015).

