6 OBJECTIVES

The primary objective of this study is to evaluate if pre-operative QST can identify if patients will have high pain intensity peri-operatively and at 6 months post-operatively. We will evaluate the intensity and chronicity of pain and the function of the descending inhibitory system through a short QST procedure before surgery and six months after surgery. In addition, we will evaluate the patient's physical and emotional functioning, and explore the potential biological underlying mechanisms at the same time points.

The secondary objective of this study is to determine if the peri-operative use of an alpha-2 adrenergic receptor agonist enhances the efficacy of the descending inhibitory system of patients with sub-optimal CPM efficacy before surgery by decreasing pain after surgery. Consequently, this pharmacological intervention may also reduce the incidence of acute and chronic pain after surgery. We will evaluate the pain intensity and the function of the descending inhibitory system through a short QST procedure six weeks after surgery and six months after surgery in patients receiving Clonidine or placebo during the perioperative period. We will also evaluate the patient's physical and emotional functioning, and explore the potential biological underlying mechanisms at the same time points.

We will also evaluate the potential biomechanical alterations in 3D related to pain in children reporting presence of back pain pre and post spine surgery.

Our hypothesis is that patients undergoing spine surgery with poor inhibitory pain response will have less pain in the immediate and long-term period when treated prophylactically with Clonidine in the perioperative period.

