9 STUDY INFORMATION

9.1 BASELINE VISIT

The expected duration for the patient's participation in the research is 6 months and will consist of a baseline visit, In-hospital visit, 6 week post-op visit and a 6 month post-op visit.

At the baseline visit, the subject will be expected to complete the following:

- ✓ Pain intensity rating (self-reported) (Wong Baker Faces Pain Scale)

- ✓ Medical History Interview (Patient History Collection Form)
- ✓ Approximately 10 mL of blood will be drawn and blood pressure will be taken
- ✓ Quantitative Sensory Testing (QST = MDT/PPT/CPM tests)

The subject will be expected to fill out the following questionnaires:

- ✓ Pain numerical rating scale for children (Baseline - 4 questions)
- ✓ State-Trait Anxiety Inventory (STAI-C)
- ✓ Pain Catastrophizing Scale (PCS-C)
- ✓ Functional Disability Index (FDI)
- ✓ Revised Children Anxiety and Depression Scale (RCADS)
- ✓ Pittsburg Sleep Quality Index (PSQI)
- ✓ Neuropathic Pain Questionnaire (DN4)
- ✓ Tampa Scale for Kinesiophobia (TSK)
- ✓ Scoliosis Research Society (SRS-30)
- ✓ Adolescent Pediatric Pain Tool (APPT)

The visit should take approximately 1 hour

Once the subject's CPM results from the baseline visit have been assessed, the subject will be categorized into one of two arms: 1) Sub-optimal endogenous inhibitory response or 2) Optimal endogenous inhibitory response. The sub-optimal group will then be randomized to either Clonidine or the placebo, and the optimal group will be also randomized to either Clonidine or the placebo.

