11.2.3.2 COVAS (COMPUTERIZED VISUAL ANALOG SCALE)

The Research Assistant will explain the CoVAS device to the subject. The CoVAS device is a sliding scale which is connected to the laptop's software. The subject is instructed to use the scale slider to indicate the intensity of their pain on a scale of 0 to 10. It is important that the subject understand that this device will not control the temperature of the test.

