11.2.4.2 THERMODE TEST BEFORE BATH

The Research Assistant will prepare the Software for the Thermode Test. The subject’s VAS50% score will be used to personalize the Thermode Test.

1. For the Thermode test, the subject’s “Left Forearm Medial” will be used. Select the site just below the site used for the pre-test.
2. This Thermode Test is for a duration of 2 minutes and the temperature remains at the subject’s VAS50% temperature throughout. Although the temperature remains constant at the subject’s VAS50%, the subject is instructed that the temperature will vary throughout the test. The subject should indicate their pain intensity with the COVAS device with “0” being no pain at all and “20” being the worst pain imaginable. Assistant feels there was an issue with the test, repeat the test.
3. The pain threshold, VAS50% and the pain tolerance should be recorded on the CPM response form.

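### Temporal summation is cited as a pre-operative predictor of acute and chronic pain, but no temporal summation score is derived or analysed; a pre-specified secondary score from the existing heat run would close the gap cheaply

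*Combined protocol and SAP*

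**What the plan says.** **Background (2.1).** The section introduces QST with "Two central mechanisms commonly assessed in the experimental setting through QST are the temporal summation (TS) and conditioning pain modulation (CPM"). For acute pain after thoracotomy it cites "enhanced pre-surgical TS, a psychophysical correlate of wind-up", together with pain scores to mechanical stimulation. For chronic pain it says "Preoperative TS level may also be a mechanistic predictor for the development of chronic postoperative pain", and separately that "efficient preoperative CPM predicted lower risk of chronic post-thoracotomy pain in adult patients". A last result, on early post-operative testing, again concerns TS.

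**Objective (6).** The primary objective is to "evaluate if pre-operative QST can identify if patients will have high pain intensity peri-operatively and at 6 months post-operatively". The next sentence speaks of the function of the descending inhibitory system.

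**Battery and classification.** Section 9.1 defines the tests as "Quantitative Sensory Testing (QST = MDT/PPT/CPM tests"), and the study plan table (12.1) lists the same three. Sections 8.1 and 9.1 classify patients by CPM result only.

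**Procedure (11.2).** Of the run before the cold bath, 11.2.4.2 says "This Thermode Test is for a duration of 2 minutes", at a constant temperature set to the patient's own VAS50%. She rates pain throughout on the CoVAS, described in 11.2.3.2 as a "sliding scale which is connected to the laptop" software. The values that 11.2.4.2 sends to the response form are pain threshold, VAS50% and tolerance.

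**Analysis (16).** The only QST-based prognostic comparison in 16.5 is sub-optimal versus optimal inhibitory response in the placebo arm. Section 16.4 mentions QST change over time in general terms. TS is not named anywhere in section 16.

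**The concern.** The objective is worded for QST as a whole, and the background gives TS at least as much predictive support as CPM. For the peri-operative part of the objective, section 2.1 cites TS and mechanical pain scores but no CPM result. The plan then carries only CPM forward as a central measure.

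The stake is the breadth of the conclusion. A null or positive CPM result answers a question about inhibition; it does not show whether facilitation, measured in the same session, predicts pain. The existing heat run could probably supply such a measure, but only if the rating trace is kept. A trace that is not saved cannot be recovered later.

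**Working it through.** **1. The plan's own figure.** Section 16.3 uses a difference of 2, SD 2.0, two-sided alpha 0.05, power 90% and rho = 1.
- n per group = 2 × (1.960 + 1.282)² × (2/2)² = 21.01, rounded up to 22.
- The repeated-measures factor (1 + 2 × rho)/3 equals 1 at rho = 1, so 22 reproduces. A derived TS score does not alter it.

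**2. TS traced through the document.**

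| Place | TS | CPM |
|---|---|---|
| 2.1, named as central mechanism | yes | yes |
| 2.1, pre-operative, acute pain | cited | not cited |
| 2.1, pre-operative, chronic pain | cited | cited |
| 9.1 and 12.1, battery | no | yes |
| 11.2, derived score, slope or early-versus-late difference | none | bath procedure given |
| 8.1, 9.1, 16.5, classification and comparisons | none | yes |
| 16.4, named predictor | none | via the 16.5 groups |

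After section 2.1 temporal summation appears only in reference titles.

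**3. What adding TS could bring.** The documents give no correlation, so these are assumptions: CPM with pain r = 0.3 (scored so that higher is worse), TS with pain r = 0.2 to 0.4, TS with CPM c = 0 or 0.3.
- R² = (0.3² + r² − 2 × 0.3 × r × c)/(1 − c²)
- partial r = (r − 0.3c)/√[(1 − 0.3²)(1 − c²)]
- power = Φ(atanh(partial r) × √(N − 4) − 1.96)

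CPM alone gives R² = 0.09. N = 150 is the planned total, used for in-hospital pain. N = 94 is 150 × 22/35 = 94.3, used for six months.

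| c | TS r | R² | partial r | Power, N=150 | Power, N=94 |
|---|---|---|---|---|---|
| 0 | 0.2 | 0.130 | 0.210 | 73% | 52% |
| 0 | 0.4 | 0.250 | 0.419 | >99% | 99% |
| 0.3 | 0.2 | 0.103 | 0.121 | 31% | 21% |
| 0.3 | 0.4 | 0.196 | 0.341 | 99% | 92% |

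Worked line for c = 0, r = 0.2: partial r = 0.2/√0.91 = 0.210; atanh = 0.2128; × √146 = 2.571; 2.571 − 1.960 = 0.611; Φ = 0.73.

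Neither N is firm. Section 16.3 equates 35 × 4 with 150, but the product is 140. It gives no dropout rate, and it says the increase from 22 to 35 also serves to limit confounding. With 140 and 22 × 4 = 88 instead, the r = 0.2 rows become 70% and 50% (c = 0), and 29% and 20% (c = 0.3).

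**4. Choice of score.** Subtracting the lowest earlier 30-second mean from the last one would not do. Two minutes hold four 30-second windows. For flat ratings with independent window noise, the expected minimum of three normal values is −0.85 SD, so the score averages +0.85 SD with no summation at all. A fixed early window has expectation zero under flat ratings.

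**The case against.** The strongest reply is that the plan narrows itself to inhibition on purpose. Section 4 calls endogenous analgesia a key mechanism and tests it by CPM. The central hypothesis in 5.1 concerns poor inhibitory pathways, the primary objective goes on to the descending inhibitory system, and both comparisons in 16.5 are defined by inhibitory response. Section 2.1 is a literature review of what is commonly measured, not a commitment to measure it. This stands, and it limits the point to the general QST wording of the objective.

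Four stronger readings are tempting, and the documents do not support them.
- **Half of the QST rationale goes untested, or three of four cited results are TS.** These are counts of mechanisms and statements. One of the three TS results comes from post-operative testing, so the pre-operative count is two TS to one CPM. Two of the TS statements share a citation label, and another also rests on mechanical pain scores.
- **The TS data are already recorded.** The slider is linked to software, but no section says the continuous trace is retained.
- **A null CPM result would be reported as QST failing to predict.** No section says so; 16.5 words its first comparison in terms of inhibitory response.
- **Power is ample.** At a partial r of 0.3 it would be about 96% (N=150) and 84% (N=94), but that is a favourable choice within an assumed range.

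It is also fair to say that the documents never describe drift over this run as a TS measure. Patients are told that the temperature will vary when it does not, so part of any drift may be expectation. Hence the label TS-type, and the secondary or exploratory status.

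**Conclusion.** The point holds as a cheap improvement, not as an error in the main design. Section 2.1 cites pre-operative TS as a predictor of acute and chronic pain, the primary objective asks about pre-operative QST, and no TS score is derived or analysed. The CPM hypothesis, allocation and clonidine comparison are unaffected.

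The size is uncertain. Under the assumed correlations R-squared rises from 0.09 to between 0.10 and 0.25. At the low end the TS term has 73% power at N=150 and 52% at N=94 if TS and CPM are uncorrelated, and 31% and 21% if they correlate at 0.3. These figures adjust for CPM only, not for arm or baseline pain, and N=94 is an assumption. A null TS result would therefore be weak evidence against TS.

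**What to change.** **In 11.2.4.2**
- State that the full CoVAS trace is exported and stored for each run.
- Reconcile the rating anchors. This section uses 0 to 20 with worst imaginable pain, whereas 11.2.3.2.2 and 11.2.4.4 use 0 to 10 with worst tolerable pain. CPM scoring across the two runs needs this as well.
- Pre-specify one TS-type score from the baseline before-bath run with fixed windows, for example the mean of the last 30 seconds minus the mean of a fixed early plateau window (not the lowest window).
- State which run counts when a test is repeated.

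**In 16.4**
- Enter the score as a continuous predictor beside CPM, labelled secondary or exploratory, for in-hospital pain (the 48-hour mean already defined in 12.1 would serve) and for six-month pain, with arm and baseline pain in the model.
- Keep classification and randomisation on CPM.
- Limit conclusions about QST to the measures analysed.

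If the sponsor prefers not to add the score, the minimum is a sentence in 2.1 saying TS is background only, together with that limit on conclusions.

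**Cost.** One export, one derived variable and one model term; no new test, visit or patient. The downside is one more secondary predictor, with modest power if its effect is small.
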